8.0 REFERENCES	

Affected Section(s)	Summary of Revisions Made	Rationale
3.2; 3.3; 3.4; 3.5; 4.0; 5.3	Study inclusion and exclusion criteria were further specified (3.2 and 3.3). Study recruitment process and strategies were further explained and described (3.5). One more study questionnaire was added (4.0). Variables to be collected were described in details (5.3).	Changes were made internally to provide more details about the study particularly about the recruitment process.
3.3; 3.5	Two study exclusion criteria omitted (3.2 and 3.3). New recruitment method added (3.5).	Changes were made internally to include a larger potential cohort and make patient identification easier for study staff and referring providers.

SUMMARY OF CHANGES FROM PREVIOUS VERSION:

PROTOCOL SUMMARY

Purpose

- Examine the feasibility of using Virtual Reality (VR) software VR Solace as a method for treating any-cause chronic pain in hospitalized patients

- Compare physiological changes during use of VR Solace to patient reported outcomes (PROs).

✤ Aims

1) To assess the effects of VR Solace on pain and anxiety as reported by the Numeric Pain Rating Scale (NPRS) and the State-Trait Anxiety Inventory 6 (STAI-6), respectively

- Measure the subsequent therapeutic response using validated survey data

- Analysis of demographic characteristics and survey data will be conducted to identify factors associated with greater therapeutic responses to VR Solace in patients with pain

Evaluate associations between medical history/lab values to patient PROs
2) To investigate any correlations between physiological changes during VR Solace use (heart rate, heart rate variability, and pupil diameter) and patient-reported outcomes.

- Demonstrate presence of physiological effects with VR Solace use
- Evaluate which physiological effects are associated with greater therapeutic response
- Research Procedures
 - Validated survey to assess pain and anxiety pre-VR
 - Administer VR Solace to patients
 - Collect real-time biodata during VR Solace session of 15 minutes
 - Repeat surveys post-VR
 - Data analysis
- Subject Population
 - Patients currently admitted at Cedars-Sinai Medical Center with chronic pain, independent of admitting diagnosis
- Duration
 - 1 visit per subject
 - Total study period of 3 months

GENERAL INFORMATION

- CSMC Co-Investigators
 - All listed on cover page
 - Any other residents to be involved
- Sponsor/Funder
 - This study is not funded

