4.0 STUDY DESIGN AND METHODS

Collection of Survey Data

 \rightarrow *Primary outcomes*: Evaluate for treatment response in pain/anxiety levels after VR Solace session (1 time)

- Validated pain survey
 - Pain Numeric Rating Scale (pre & post-VR)
- Validated anxiety survey
 - Full or 6-question abridged version of State-Trait Anxiety Inventory (pre & post-VR)

→ Secondary outcome: Assess for physiological changes during VR Solace use (heart rate, heart rate variability, and pupil diameter)

- Compare the average physiologic measures (3 listed above) of the first minute with average of last minute of VR use (15 minutes total, not including pre- and post-VR survey time)
- Correlation of the changes in average and survey data/patient-reported outcomes
- \rightarrow *Covariates*: Consider using these survey variables as covariates in multivariable regression models
- System Usability Scale subjective assessments of device/system usability
- Simulator sickness questionnaire (SSQ) Assessing motion sickness + presence survey
- Immersive Tendencies Questionnaire

✤ Collection of Biodata

 \rightarrow Directly from VR Solace device

• Heart rate, heart rate variability, pupil diameter changes – calculation of averages

• Use as covariates in multivariable regression models

Data Analysis

- → Multivariable linear regression models
 - Change in pain/anxiety scores as outcomes continuous variable
 - Covariates of demographic factors, comorbidities, biodata, other survey data (System Usability Scale, Immersive Tendencies Questionnaire)

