7.0 STATISTICAL CONSIDERATIONS

7.1 STUDY OUTCOME MEASURES

Outcomes will be continuous—change in pain/anxiety levels in response to VR Solace treatment session. The levels will be measured by validated scales, and changes will be calculated based on pre-session and post-session survey responses. Secondary outcomes will also be continuous, as change in averages of first and last minute of the VR Solace session (not including pre- and post-VR survey time).

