7.2 SAMPLE SIZE CONSIDERATIONS

• A paired t-test was used to calculate power. The desired power is 80% and 0.05 was used as the significance level.

- To achieve a moderate to large effect of 0.5, we estimate to recruit a sample of 34 patients, and to achieve a larger effect of 0.8, we estimate to recruit a sample of 16 patients.
- No measures to decrease bias/precision such as blinding of staff will be performed, however study protocol will be followed strictly for all subjects in same hospital settings.

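### Aim 2 correlates raw physiological change with raw symptom change and specifies no adjustment for either starting value, so a shared starting state can produce a correlation by itself

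*Combined protocol and SAP*

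**What the plan says.** Section 4.0 (secondary outcome) takes heart rate, heart rate variability and pupil diameter and plans to "Compare the average physiologic measures (3 listed above) of the first minute with average of last minute of VR use". The next bullet gives the Aim 2 analysis: "Correlation of the changes in average and survey data/patient-reported outcomes". Section 7.1 defines the physiological outcome as "change in averages of first and last minute of the VR Solace session" and the pain and anxiety outcomes as changes from the pre-session to the post-session survey. Section 2.0 confirms that the association sought is between the two changes. The Protocol Summary states the use of the result under Aim 2: "Evaluate which physiological effects are associated with greater therapeutic response".

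Section 4.0 also lists a multivariable regression with change in pain or anxiety as outcome. Its covariates include biodata, described as changes and averages. Neither the first-minute value nor the pre-VR score is named there, and the regression is listed apart from the correlation.

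**The concern.** A change is the end value minus the start value, so each of the two changes carries its own start with a negative sign. A patient who begins the session tense may have both a high first-minute heart rate and a high pre-VR anxiety score, and both then have room to fall. Across patients the two falls will correlate even if what happens during the session is unrelated. For a measure that runs lower when a patient is tense, the sign reverses and the size is the same.

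Aim 2 would read such a correlation as identifying the physiological effects that accompany a better therapeutic response, and section 1.0 hopes to predict individual response from biodata. The planned analysis offers no view of how much of the correlation comes from the starting values, although both are collected for every patient.

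**Working it through.** **The plan's own figure.** Section 7.2 states that "A paired t-test was used to calculate power", with 80% power and a 0.05 significance level. A two-sided paired t-test at effect size 0.5 needs 34 patients (power 80.8%), which matches. At 0.8 it needs 15; the stated 16 gives 84.8%. The sample size is not in dispute, but it does not cover a correlation. At n = 34, the 5% critical value of |r| is 0.34, and 80% power needs |r| of about 0.46.

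**Inputs.** The documents give no correlation between starting values and none between start and end. Everything below is assumed, with no link between the two responses beyond the start. Rates of a positive 5% test use Fisher z: with z = √(n − 3) × atanh(r), the rate is Φ(z − 1.96) + Φ(−z − 1.96). At n = 34, √31 = 5.57.

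**Model A: each end value depends only on its own start.** End = b × start + independent noise, start variance 1, noise variance v, correlation of starts c. Then

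corr(changes) = c(1 − b)² / [(1 − b)² + v].

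- Equal variances at start and end (v = 1 − b²): this reduces to c(1 − b)/2. With c = 0.3, b = 0.7 it is 0.045 (positive in 6% of studies). With c = 0.6, b = 0.3 it is 0.21 (22%).
- Half that noise, c = 0.6, b = 0.3: v = 0.91/2 = 0.455, so 0.6 × 0.49/0.945 = 0.31 (43%).
- Adjusted for the pre-VR score alone, the first-minute value alone, or both: 0 in every case, with the test at 5%.

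**Model B: a shared starting state fades.** Start = stable part (variance 1) + shared transient (variance s) + noise (variance v). End = stable part + noise. Stable parts are independent between measures.

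- Raw: s/(s + 2v). With s = 0.25, v = 0.5: 0.25/1.25 = 0.20. With s = 1, v = 0.25: 1/1.5 = 0.67.
- Implied correlation of starts: s/(1 + s + v), which is 0.14 and 0.44.
- Given the pre-VR score, with a = 1 + s + v, the partial covariance is s − s(a − 1)/a. The partial variances are s + 2v − s²/a (physiology) and s + 2v − (a − 1)²/a (symptom). Low end: 0.143/√(1.214 × 0.929) = 0.13. High end: 0.444/√(1.056 × 0.806) = 0.48.
- Given both starts: s / [(1 + v)(a² − s²) − a]. Low end: 0.25/(1.5 × 3 − 1.75) = 0.09. High end: 1/(1.25 × 4.0625 − 2.25) = 0.35.

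At n = 34 a 5% test is positive in about 20% to 99% of studies raw, and in about 8% to 51% with both starts.

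**Separate check.** With equal variances, transient shared arousal, starts correlated 0.3 and start-to-end correlation 0.5, the raw correlation is 0.30 (positive in 41% at n = 34; simulation agrees). It is 0.18 with the first-minute value only and 0.11 (9%) with both starts.

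**Precision.** If first and last minute have equal variances and correlate ρ, adjusting for the first minute leaves a fraction (1 + ρ)/2 of the variance of the change: 0.95 at ρ = 0.9 and 0.75 at ρ = 0.5. Physiology is the predictor here. For a given residual outcome variance, the standard error of its coefficient therefore rises by 1/√0.95 to 1/√0.75, about 3% to 15%.

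**The case against.** The other side has a good case, and much of it stands.

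- *The regression may already cover this.* The biodata covariates could include a first-minute average. A reader might infer that the plan excludes adjustment; the text supports only that none is specified.
- *The first-minute term adds nothing in Model A.* Correct: the pre-VR score alone brings the correlation to 0. A reader might credit the 43% to the missing first-minute value. That is not supported, and the figure also needs the halved noise variance; with equal variances the maximum is 22%.
- *In Model B the remedy is partial.* Correct: the first-minute term moves 0.13 to 0.09 and 0.48 to 0.35.
- *Model B is not purely an artefact.* If tension fades and both anxiety and heart rate fall with it, that joint calming is arguably what Aim 2 looks for, and adjustment may remove real signal. This is why the raw correlation should stay in the report.
- *The first minute is not a pre-exposure baseline.* Section 4.0 places it within VR use, so it may already hold early response or headset novelty.
- *Aim 2 is exploratory.* It is, and a raw correlation is a legitimate description. That limits the weight of the point, but a second analysis costs little.

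A reader might also expect adjustment to gain precision. For the physiology coefficient, the calculation above points the other way.

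**Conclusion.** The point holds as a modest improvement to a secondary, exploratory analysis. The planned correlation uses two simple differences with no specified adjustment for either start, and correlated starts alone can produce a correlation between them. How large it would be in this study is unknown: under Model A with low inputs the positive rate is about one point above the nominal 5%, while under Model B it can be most of the correlation a study of 34 could detect or more. The pre-VR score does all the work in Model A. The first-minute value matters only in Model B, and only in part.

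The documents do not support the stronger conclusions that the Aim 2 correlation is invalid or that the adjusted result would isolate a response to VR. The study has no control group, so spontaneous settling remains an explanation under either analysis.

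**What to change.** In section 4.0, keep the raw change-change correlation and add, for each physiological measure separately and for pain and anxiety in turn, a regression of the post-VR score on the pre-VR score, the first-minute value and the last-minute value. Report the last-minute coefficient (or partial correlation) with its 95% CI beside the raw correlation. With the first-minute value in the model, this coefficient equals that of the physiological change.

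State in advance that a raw correlation which shrinks on adjustment may reflect a shared starting state. State also that the first minute is already during VR use, and that without a control group neither analysis separates response to VR from settling.

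The cost is wording only; all four values are already collected. Two degrees of freedom are used (four parameters, leaving 34 − 4 = 30), and the interval for the physiology coefficient may widen by the 3% to 15% shown above.

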Therefore, the purpose of this prospective, observational study is to assess the therapeutic response to VR Solace in patients with chronic pain and anxiety using real-time clinical and survey data. Secondly, with use of relatively more complex biodata, this study can establish a possible association between the patient-reported changes in pain or anxiety levels with several real-time physiological measurements during VR Solace use. This study hopes to pave way not only in developing a standard VR therapy regimen for chronic pain and anxiety, but also in formulating a prediction of an individual's therapeutic response to VR based on biodata and clinical factors.

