5.3 VARIABLES COLLECTED

The following data points/variables will be collected:

- Age
- Education
- Gender
- Employment
- Marital status
- Income
- Household size
- Primary admitting diagnosis
- Primary referral diagnosis (provider reported or ICD-10 coded)
- Race
- Ethnicity
- Surgical history (any pain related surgery)
- Social history drug/opiate use)
- Medications/treatments (opioids, MME, start date-end date for at least 3 months)
- Survey data (pre & post-VR session) described above
- Real-time biodata obtained through VR device heart rate, heart rate variability, pupil diameter changes

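### The regressions in 4.0 set no limit on covariates while the study is sized at 34 or 16 patients for a paired t-test only; if all listed groups enter one model (about 15 terms, assumed), it is saturated at 16 and leaves 18 residual degrees of freedom at 34.

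*Combined protocol and SAP*

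**What the plan says.** Under Data Analysis, section 4.0 names multivariable linear regression, with change in pain and change in anxiety as continuous outcomes. The right-hand side is given by group: "Covariates of demographic factors, comorbidities, biodata, other survey data (System Usability Scale, Immersive Tendencies Questionnaire". Elsewhere in 4.0, the three biodata measures (heart rate, heart rate variability, pupil diameter) are to be used as covariates in these models without qualification. The survey scales, there including a simulator sickness and presence questionnaire, are only to be considered as covariates.

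Section 5.3 lists the variables collected. Nine are demographic or socioeconomic, down to items such as "Household size". No item is called comorbidities.

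On size, 7.2 states: "A paired t-test was used to calculate power". It then gives two targets: "we estimate to recruit a sample of 34 patients, and to achieve a larger effect of 0.8, we estimate to recruit a sample of 16". It does not say which target applies, and nothing sizes the regression.

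The regression serves a stated purpose. Aim 1 in the Protocol Summary wants to find characteristics linked to a larger response, and section 1.0 hopes the work will lead towards predicting an individual's "therapeutic response to VR based on biodata and clinical factors".

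**The concern.** A least-squares model with many terms and few patients absorbs noise. Here the list of terms is open and the sample was chosen for a different and much less demanding analysis. Following the plan literally could give a model that cannot be tested at all, or one with an impressive R-squared and some nominally significant factors arising by chance. Because the covariate set is not fixed in advance, the choice of terms made after seeing the data could also decide which factors are reported. At stake is the factor-finding part of Aim 1 and any later claim about prediction.

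**Working it through.** **1. The plan's own figure.** The inputs, from 7.2, are: "The desired power is 80% and 0.05 was used as the significance level". Sidedness is not stated; I took two-sided. Power of the paired t-test comes from the noncentral t with n − 1 degrees of freedom and noncentrality d√n.

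- d = 0.5: the smallest n is 34 (power 80.8%), matching the plan.
- d = 0.8: the smallest n is 15 (power 82.1%). The plan's 16 gives 84.8%, which is close enough to count as reproduced.

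So 34 and 16 are sound for the paired comparison. They carry no allowance for covariates.

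**2. How many terms?** The plan gives no number, so this is an assumption. One degree of freedom per item gives:

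- demographics in 5.3: age, education, gender, employment, marital status, income, household size, race, ethnicity = 9
- biodata in 4.0 = 3
- System Usability Scale and Immersive Tendencies Questionnaire = 2
- comorbidities, number not stated, at least 1

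9 + 3 + 2 + 1 = 15. Multi-category race, employment or marital status, more comorbidities, or the simulator sickness questionnaire would raise it. Selecting among the demographics would lower it. With one demographic and one comorbidity term it would be 1 + 1 + 3 + 2 = 7.

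**3. Fit under no association.** With an intercept and p terms, the residual degrees of freedom are n − p − 1, and the expected R-squared when nothing is related to the outcome is p/(n − 1).

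| Terms p | Residual df, n = 16 | Null R², n = 16 | Residual df, n = 34 | Null R², n = 34 |
|---|---|---|---|---|
| 3 | 12 | 20% | 30 | 9% |
| 5 | 10 | 33% | 28 | 15% |
| 7 | 8 | 47% | 26 | 21% |
| 10 | 5 | 67% | 23 | 30% |
| 14 | 1 | 93% | 19 | 42% |
| 15 | 0 | 100% | 18 | 45% |
| 20 | not estimable | – | 13 | 61% |

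**4. Simulation check.** I used 10,000 null data sets per setting, with independent normal covariates and outcome. At n = 34 and p = 15, mean R-squared was 45.6% (5th to 95th percentile 26% to 65%). Each coefficient test rejected 5.0% of the time, the overall F test 4.9%, and mean adjusted R-squared was 0.00. At least one covariate had p < 0.05 in 42% of data sets; with 5 terms the figure was 21%. There are two outcomes. If they were independent, the chance of a false factor in either would be 1 − (1 − 0.424)² = 67% at 15 terms and 1 − (1 − 0.205)² = 37% at 5. Correlation between pain and anxiety changes would lower both.

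**5. Precision.** For independent normal covariates and a fixed residual variance, a coefficient's variance is proportional to 1/(n − p − 2). Against a two-term model at n = 34, the standard error ratio at 15 terms is √(30/17) = 1.33. At 24 terms, an upper assumption if categories are split, it is √(30/8) = 1.94. Correlated covariates would make this worse; covariates that truly explain outcome variance would offset some of it.

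**The case against.** The best defence is that the plan does not commit to one 15-term model. It names groups, speaks of models in the plural, and only suggests considering the survey scales. Section 5.3 lists what is collected, not what is modelled. This stands: 15 is an assumption, and exact fit at 16 patients needs at least that many terms. At 14 one residual degree of freedom remains. It does not remove the point, because at 16 patients even 5 terms give a null R-squared of 33%, and no text keeps the count that low.

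A reader might infer that coefficient tests at 34 patients are invalid. They are not: each keeps its 5% level, and adjusted R-squared is correctly centred on zero. The problem at 34 is multiplicity, precision and the raw R-squared.

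A reader might also infer that regression is the only analysis of the outcomes, so that Aim 1 as a whole fails. The documents do not support this. Section 4.0 also plans correlations of physiological change with patient-reported outcomes, 7.2 is built on a paired comparison, and factor-finding is one part of Aim 1.

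Nor does section 1.0 promise a prediction model from this study. It hopes to open the way to one.

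A last objection concerns the remedy. Testing 15 factors one at a time without correction is no safer: with independent null factors, 1 − 0.95¹⁵ = 54% against about 42% in the joint model. That is right, and the fix below allows for it.

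**Conclusion.** The concern holds as a gap in pre-specification with a measurable cost. The covariate list is open, and the sample was set for another analysis. Under the assumption that all listed groups enter one model at about 15 terms, the model is saturated at 16 patients. At 34 it leaves 18 residual degrees of freedom, with an expected null R-squared of 45%, standard errors about 1.33 times those of a two-term model, and about a 42% chance of at least one false factor per outcome. With fewer terms the problem shrinks but remains material at 16. Which sample target applies is not stated, so the saturated case cannot be ruled out. The paired pre-to-post comparison is not affected. This is a cheap improvement to the plan and does not undermine the study as a whole.

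**What to change.** In 4.0, Data Analysis, replace the open covariate list with one of two options:

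- **A short pre-named model for each outcome, scaled to the final sample.** For example, about three terms at 34 patients and one at 16, including the pre-VR score. This keeps the expected null R-squared below 10% (3/33 = 9%; 1/15 = 7%). The 10% mark is a working judgement, not a fixed rule.
- **One ridge or lasso fit per outcome**, reporting cross-validated R-squared.

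Report the remaining factors in 5.3, and the Aim 2 correlations of the three biodata changes with the outcomes, as exploratory estimates with 95% confidence intervals. Either control multiplicity (Holm or false discovery rate) or make no significance claims. Keeping the biodata here means that Aim 2 is still served.

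Report adjusted or optimism-corrected R-squared in place of the raw figure. State that no claim about individual prediction will be made without optimism-corrected performance (bootstrap or cross-validation). Say in 7.2 which sample target applies and that it covers the paired comparison only.

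The cost is wording: no extra patients or data. The downside is fewer mutually adjusted estimates and a more modest factor-finding claim.

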5.0 DATA COLLECTION AND MANAGEMENT

5.1 DATA PROCUREMENT

- Biodata will be collected by the VR headset during the session.
- Patient-reported outcome data will be collected by surveys administered to the study participants.

5.2 TIME PERIOD OF DATA UNDER REVIEW

- Data under review will be of de-identified data
- Real-time data will be collected at time of VR sessions, which will be held though an estimated time of 6 months. Data will be collected prospectively.
- Information will be kept for an indefinite time.

5.3 VARIABLES COLLECTED

The following data points/variables will be collected:

- Age
- Education
- Gender
- Employment
- Marital status
- Income
- Household size
- Primary admitting diagnosis
- Primary referral diagnosis (provider reported or ICD-10 coded)
- Race
- Ethnicity
- Surgical history (any pain related surgery)
- Social history drug/opiate use)
- Medications/treatments (opioids, MME, start date-end date for at least 3 months)
- Survey data (pre & post-VR session) described above
- Real-time biodata obtained through VR device heart rate, heart rate variability, pupil diameter changes

